#### 9.5.2.1.3 *Serious Adverse Events*

An SAE is any untoward medical occurrence that at any dose:

- Results in death
- Is life threatening
- Requires inpatient hospitalization or prolongation of existing hospitalization
- Results in persistent or significant disability/incapacity, or
- Is a congenital anomaly/birth defect

Important medical events that may not result in death, be life threatening, or require hospitalization may be considered serious when, based on appropriate medical judgment, they may jeopardize the patient and may require medical or surgical intervention to prevent one of the outcomes listed in this definition. Examples of such medical events include allergic bronchospasm requiring intensive treatment in an emergency room or at home, blood dyscrasias or convulsions that do not result in patient hospitalization, or the development of IP dependency or drug abuse.

Emergency room visits that do not result in hospitalization should be evaluated for one of the other serious outcomes to determine whether they qualify as SAEs.

Preplanned hospitalizations (eg, elective procedures for pre-existing conditions that did not worsen, such as cosmetic surgery and hysterectomy) are excluded from SAE reporting.

#### *9.5.2.1.4 Reporting Adverse Events and Serious Adverse Events*

At each visit, patients are to be queried regarding any AEs or SAEs that have occurred since the previous visit. Patients will be asked to volunteer information with a nonleading question such as, “How do you feel since your last visit?” Study center personnel will record all pertinent information in the patient’s eCRF.

All AEs must be recorded on the appropriate AE reporting page of the patient’s eCRF whether or not they are considered causally related to the IP.

For every AE, the investigator must:

- Provide an assessment of the seriousness of the event (ie, is it an SAE?), as well as the severity and casual relationship
- Document all actions taken with regard to the IP
- Detail any other treatment measures taken for the AE
- Document the outcome of the AE

In addition, patients are to be reminded, as described in the ICF and in accordance with Section 9.5.2.1, to notify study center personnel of any AEs occurring during the 30-day poststudy period. Any AEs reported by the patient (or patient representative) during this period are to be recorded in original source documents. AEs are also to be recorded in the eCRF if at least one of the following conditions is met: 1) the event meets the criteria for an SAE (see Sections 9.5.2.1.3 and 9.5.2.1.4), and/or 2) the event is judged by the investigator to be potentially causally related to IP (Section 9.5.2.1.1).

Any AEs that are ongoing at the time of the final protocol-defined study visit will be followed until the condition returns to prestudy status, has resolved or stabilized, or can be explained as being unrelated to the IP. If a follow-up visit is deemed necessary for appropriate safety surveillance, it will take place within 30 days of the final protocol-defined study visit.

**9.5.2.2 Immediate Reporting of Serious Adverse Events**

The sponsor is required to inform worldwide regulatory authorities of SAEs that meet specific criteria. Therefore, the sponsor must be notified immediately regarding any SAE that occurs after informed consent is obtained.

Within 24 hours of learning of any AE that meets one of the criteria for an SAE, the study center personnel must report the event to Global Drug Safety on the SAE Form for Clinical Trials. The Study Physician may also be notified by telephone.

If, during follow-up, any nonserious AE worsens and eventually meets the criteria for an SAE, that AE should be recorded as a new SAE.

The study center must transmit the SAE Form for Clinical Trials to the SAE email address or fax number shown below. Even if an initial report is made by telephone, the SAE Form for Clinical Trials completed with all available details must still be emailed or faxed within 24 hours of knowledge of the event at the study center.

Supplemental information should be submitted as soon as available and may include laboratory results, radiology reports, progress notes, hospital admission and emergency room notes, holding and observation notes, discharge summaries, autopsy reports, and death certificates.

The investigator is expected to take all therapeutic measures necessary for resolution of the SAE. Any medications or procedures necessary for treatment of the SAE must be recorded on the appropriate pages of the patient's eCRF. All SAEs are to be followed by the study staff until resolution or until the SAE is deemed stable. ***The sponsor may contact the study center to solicit additional information or follow up on the event.***

[Redacted]

[Redacted]

[Redacted]

**9.5.2.3 Reporting of Pregnancies Occurring During the Study**

Study center personnel must report every pregnancy from the time the patient signs the ICF until 30 days after the last dose of IP. Within 24 hours of learning of the pregnancy, the study center personnel must report the event to Global Drug Safety on the Clinical Trial Pregnancy Form and email or fax it to the SAE/Pregnancy email address or fax number provided in Section 9.5.2.2, even if no AE has occurred. Pregnancies in female partners of male patients occurring during the time frame described above must also be reported.

Any pregnancy of a patient treated with IP must be followed to term and the outcome reported by completing a follow-up Clinical Trial Pregnancy Form. If the pregnancy is associated with an SAE (eg, if the mother is hospitalized for hemorrhage), a separate SAE Form for Clinical Trials must be filed as described in Section 9.5.2.2, with the appropriate serious criterion (eg, hospitalization) indicated in addition to the pregnancy form.

[REDACTED]

[REDACTED]

[REDACTED]

[REDACTED]

[REDACTED]

[REDACTED]

[REDACTED]

[REDACTED]

[REDACTED]

[REDACTED]

[Redacted text block]

[Redacted text block]

[Redacted text block]

[Redacted text block]

[Redacted text block]

[Redacted text block]

[Redacted text block]

[Redacted text block]

[Redacted text block]

[REDACTED]

[REDACTED]

[REDACTED]

[REDACTED]

[REDACTED]

[REDACTED]

[REDACTED]

[REDACTED]

[REDACTED]

[REDACTED]

[REDACTED]

[REDACTED]

[REDACTED]

[REDACTED]

[REDACTED]

[REDACTED]

[REDACTED]

[REDACTED]

[REDACTED]

[REDACTED]

[REDACTED]

[REDACTED]

[REDACTED]

[REDACTED]

[REDACTED]

[REDACTED]

[REDACTED]

[REDACTED]

[REDACTED]

[REDACTED]

[REDACTED]

[REDACTED]

[REDACTED]

[REDACTED]

[REDACTED]

[REDACTED]

[REDACTED]

[REDACTED]

[REDACTED]

[REDACTED]

[REDACTED]

[REDACTED]

- 1 [REDACTED]
- 1 [REDACTED]
- 1 [REDACTED]
- 1 [REDACTED]
- 1 [REDACTED]
- 1 [REDACTED]
- 1 [REDACTED]
- 1 [REDACTED]
- 1 [REDACTED]
- 1 [REDACTED]
- 1 [REDACTED]
- 1 [REDACTED]
- 1 [REDACTED]
- 1 [REDACTED]
- 1 [REDACTED]
- 1 [REDACTED]

[REDACTED]

[REDACTED]

[REDACTED]

[REDACTED]

[REDACTED]

[REDACTED]

[REDACTED]

[REDACTED]

[REDACTED]

[REDACTED]

[REDACTED]

[REDACTED]

[REDACTED]

[REDACTED]

[REDACTED]

[REDACTED]

[REDACTED]

[REDACTED]

[REDACTED]

[REDACTED]

[REDACTED]

[REDACTED]

[REDACTED]

[REDACTED]

[REDACTED]

[REDACTED]

[REDACTED]

[REDACTED]

[REDACTED]

[REDACTED]

[REDACTED]

[REDACTED]

[REDACTED]

[REDACTED]

[REDACTED]

[REDACTED]

[REDACTED]

[REDACTED]

[REDACTED]

[REDACTED]

[REDACTED]

[REDACTED]

- | [REDACTED]
- | [REDACTED]
- | [REDACTED]
- | [REDACTED]
- | [REDACTED]
- | [REDACTED]
- | [REDACTED]
- | [REDACTED]
- | [REDACTED]
- | [REDACTED]
- | [REDACTED]
- | [REDACTED]

[REDACTED] [REDACTED]  
[REDACTED]

- | [REDACTED]
- | [REDACTED]
- | [REDACTED]
- | [REDACTED]
- | [REDACTED]
- | [REDACTED]
- | [REDACTED]
- | [REDACTED]

- | [REDACTED]
- | [REDACTED]
- | [REDACTED]

[REDACTED]

[REDACTED]

- | [REDACTED]
- | [REDACTED]

| [REDACTED]

| [REDACTED]

| [REDACTED]

| [REDACTED]

| [REDACTED]

| [REDACTED]

| [REDACTED]

| [REDACTED]

| [REDACTED]

| [REDACTED]

| [REDACTED]

| [REDACTED]

- | [REDACTED]
- | [REDACTED]
- | [REDACTED]
- | [REDACTED]
- | [REDACTED]
- | [REDACTED]
- | [REDACTED]
  
- [REDACTED]
- [REDACTED]
- [REDACTED]
  
- | [REDACTED]
- | [REDACTED]
- | [REDACTED]
- | [REDACTED]
- | [REDACTED]
- | [REDACTED]
- | [REDACTED]
- | [REDACTED]
- | [REDACTED]
- | [REDACTED]
- | [REDACTED]

- [REDACTED]
- [REDACTED] [REDACTED]
- [REDACTED]
- [REDACTED]
- [REDACTED]
- [REDACTED]
- [REDACTED]
- [REDACTED]
- [REDACTED]
- [REDACTED]
- [REDACTED]
- [REDACTED]
- [REDACTED]
- [REDACTED]
- [REDACTED]
- [REDACTED]
- [REDACTED]
- [REDACTED]
- [REDACTED]
- [REDACTED]

[REDACTED]

[REDACTED]

[REDACTED]

[REDACTED]

[REDACTED]

[REDACTED]

[REDACTED]

[REDACTED]

[REDACTED]

[REDACTED]

[REDACTED]

[REDACTED]

[REDACTED]

[REDACTED]

[REDACTED]

[REDACTED]

- [REDACTED]
- | [REDACTED]
- | [REDACTED]
- | [REDACTED]
- | [REDACTED]
- | [REDACTED]
- | [REDACTED]
- | [REDACTED]

[REDACTED]

[REDACTED]

[REDACTED]

- | [REDACTED]
- | [REDACTED]
- | [REDACTED]
- | [REDACTED]

[Redacted text block consisting of multiple lines of blacked-out content]

- [REDACTED]
- | [REDACTED]
- | [REDACTED]
- | [REDACTED]
- | [REDACTED]
- | [REDACTED]
- | [REDACTED]
- | [REDACTED]
- [REDACTED] [REDACTED]
- [REDACTED]
- | [REDACTED]
- | [REDACTED]
- | [REDACTED]
- | [REDACTED]
- | [REDACTED]
- | [REDACTED]
- | [REDACTED]
- | [REDACTED]
- | [REDACTED]
- | [REDACTED]
- | [REDACTED]
- | [REDACTED]
- | [REDACTED]
- | [REDACTED]

- | [REDACTED]
- | [REDACTED]
- | [REDACTED]
- | [REDACTED]
  
- [REDACTED] [REDACTED]  
[REDACTED]
- | [REDACTED]
- | [REDACTED]
- | [REDACTED]
- | [REDACTED]
- | [REDACTED]
- | [REDACTED]
- | [REDACTED]
- | [REDACTED]
- | [REDACTED]
- | [REDACTED]
- | [REDACTED]
- | [REDACTED]
- | [REDACTED]
- | [REDACTED]
- | [REDACTED]
- | [REDACTED]
- | [REDACTED]

- | [REDACTED]
- | [REDACTED]
- | [REDACTED]
- | [REDACTED]
- | [REDACTED]
- | [REDACTED]
- | [REDACTED]
- | [REDACTED]
- | [REDACTED]
- | [REDACTED]
- | [REDACTED]
- | [REDACTED]
- | [REDACTED]
- | [REDACTED]
- | [REDACTED]
- | [REDACTED]
- | [REDACTED]
- | [REDACTED]
- | [REDACTED]
- | [REDACTED]
- | [REDACTED]
- | [REDACTED]
- | [REDACTED]
- | [REDACTED]
- | [REDACTED]
- | [REDACTED]
- | [REDACTED]

• [REDACTED]

- | [REDACTED]
- | [REDACTED]
- | [REDACTED]
- | [REDACTED]
- | [REDACTED]
- | [REDACTED]
- | [REDACTED]
- | [REDACTED]
- | [REDACTED]
- | [REDACTED]
- | [REDACTED]

[REDACTED] [REDACTED]

[REDACTED]

- | [REDACTED]
- | [REDACTED]
- | [REDACTED]
- | [REDACTED]

[REDACTED]

**9.5.5.5            *Unscheduled Visits***

Unscheduled visits can be performed if safety concerns arise and at the discretion of the investigator. Additional examinations may be performed as necessary to ensure the safety and well-being of the patients during the study.

## **9.6 DATA QUALITY ASSURANCE**

### **9.6.1 Data Monitoring**

Before any patient enters the study, a representative of the sponsor will meet with the investigator and the study center staff to review the procedures to be followed during the study. Electronic data capture (EDC) functionality training is provided via computer-based training to train investigators and authorized designees on recording the data in the eCRFs using the EDC system. After the first patient is enrolled, the sponsor representative, a Regional Site Manager or designee, will periodically monitor the progress of the study by conducting on-site visits. This Regional Site Manager or designee will review query statuses remotely, possibly warranting more frequent communication and/or study center visits with the investigator and the study center staff. The investigator will make available to the Regional Site Manager or designee source documents (written notes and electronic medical records, if used), signed consent forms, and all other study-related documents. The investigator and the study center staff will be responsible for data entry of patient data into the eCRFs via the EDC system, resolving data queries generated via the EDC system and providing missing or corrected data. The investigator or designee will be responsible for approving all changes performed on the data, and endorsing the patient data within the EDC system. This approval method will include applying an electronic signature linked to a uniquely assigned username and password that together will represent a traditional handwritten signature used in the past.

### **9.6.2 Data Recording and Documentation**

Data collection will involve the use of the EDC system, to which only authorized personnel will have access. Patient's data are to be entered into the EDC system by the investigator or designee using their assigned EDC user account. After data entry into the EDC system by the investigator or designee, a combination of manual and programmatic edit checks will be used to review the data for completeness, logic, and adherence to study protocol. As a result of these edit checks, data monitoring, and reviews, queries may be electronically issued to the study center and should be answered electronically via the EDC system.

Each query will carry identifying information (assigned username, date, and time) to assist the sponsor and the investigator on the origin of the data clarification request and the response provided by the investigator. All data changes made to the patient's data via a data query will be approved by the investigator prior to final database lock.

After all data have been reviewed and all issues have been resolved, the database will be locked.

All data collected in the context of this study will be stored and evaluated per regulatory requirements and applicable guidance for electronic records. Also, data will be stored and evaluated in such a way as to guarantee patient confidentiality in accordance with the legal stipulations applying to confidentiality of data. Study records (eg, copies of eCRFs, laboratory reports, regulatory documents) will be retained at the study center, along with adequate source documentation, according to FDA and ICH requirements. All study records must be available for inspection by the sponsor, its authorized representatives, the FDA, or other health authorities.

[REDACTED]. Source documents will be used at the study centers and may include a patient's medical record, hospital charts, clinic charts, the investigator's patient study files, as well as the results of diagnostic tests such as laboratory tests, ECGs, etc. A centralized clinical laboratory will be used for the analysis of all blood samples. Additional information on the collection and handling of samples is detailed in the Lab Procedure Manual.

## **9.7 STATISTICAL METHODS AND DETERMINATION OF SAMPLE SIZE**

### **9.7.1 Analysis Populations**

Four populations will be considered in the statistical analysis of the study, as specified in the following subsections.

#### **9.7.1.1 *Open-label Safety Population***

The Open-label Safety Population will consist of all patients in the Screened Population who received at least 1 dose of open-label rapastinel during the OLTP of the study.

#### **9.7.1.2 *Open-label Modified Intent-to-Treat Population***

The Open-label modified Intent-to-Treat (Open-label mITT) Population will consist of all patients in the Open-label Safety Population who had at least 1 postbaseline assessment of the MADRS during the OLTP of the study.

#### **9.7.1.3 *Double-Blind Safety Population***

The Double-blind Safety Population will consist of all patients in the randomized patients who received at least 1 dose of double-blind IP.

#### **9.7.1.4 Double-Blind Modified Intent-to-Treat Population**

The Double-blind modified Intent-to-Treat (Double-blind mITT) Population will consist of all patients in the Double-blind Safety Population who had at least 1 postrandomization assessment of the MADRS or the CGI-S during the DBTP of the study.

#### **9.7.1.5 Pharmacokinetic Population**

The PK Population will consist of all patients in the Safety Population with at least 1 evaluable PK sample.

#### **9.7.2 Patient Disposition**

The number and percentage of patients who entered the OLTP, who prematurely discontinued from the OLTP, who completed the OLTP, who met or did not meet the criteria to enter the DBTP at the end of the OLTP, and who entered the DBTP will be summarized overall and by reasons for premature discontinuation for all enrolled patients in the OLTP. Similarly, the number and percentage of patients who completed the DBTP and who prematurely discontinued from the DBTP will be summarized overall, by double-blind treatment group, and by reasons for premature discontinuation for the all randomized patients in the DBTP.

#### **9.7.3 Demographics and Other Baseline Characteristics**

Demographic parameters and other baseline characteristics (eg, age, race, ethnicity, sex, weight, height, body mass index) will be summarized overall for the Open-label mITT Populations and by treatment group for the Double-blind modified ITT population.

#### **9.7.4 Extent of Exposure and Treatment Compliance**

##### **9.7.4.1 Extent of Exposure**

Exposure to open-label rapastinel for the Open-label Safety Population during the OLTP will be summarized for treatment duration, calculated as the number of days from the date of the first dose of open-label rapastinel taken to the date of the last dose taken during the OLTP, inclusive. Descriptive statistics (number of patients, mean, SD, minimum, median, and maximum) will be presented.

Exposure to double-blind IP for the Double-blind Safety Population during the DBTP will be summarized for treatment duration, calculated as the number of days from the date of the first dose of double-blind IP taken to the date of the last dose taken during the DBTP, inclusive. Descriptive statistics (number of patients, mean, SD, minimum, median, and maximum) will be presented by treatment group.

#### **9.7.4.2 Prior and Concomitant Medication**

*Prior medication* is defined as any medication started before the date of first dose of open-label IP. *Concomitant medication* during the OLTP is defined as any medication taken on or after the date of the first dose of open-label IP during the OLTP. Concomitant medication during the DBTP will be defined as any medication taken on or after the date of the first dose of double-blind IP.

The use of prior medication will be summarized by the number and percentage of patients receiving each medication within each therapeutic class for the Open-label Safety Population. The use of concomitant medications during the OLTP will be summarized by the number and percentage of patients receiving each medication within each therapeutic class for the Open-label Safety Population. The use of concomitant medications during the DBTP will be summarized by treatment group by the number and percentage of patients receiving each medication within each therapeutic class for the Double-blind Safety Population. Multiple use of the same medication by a patient will only be counted once.

#### **9.7.4.3 Measurement of Treatment Compliance**

*Dosing compliance* for a specified period will be defined as the total number of IV doses actually taken by a patient during that period divided by the number of IV doses that were expected to be taken during the same period multiplied by 100. The total number of IV doses actually taken during a specific time period is calculated as the sum of IV doses taken during that period as obtained from the study medication record. The number of IV doses expected to be taken for a specific treatment period will be the number of weeks in that period.

Descriptive statistics for open-label IP compliance will be presented for the OLTP for the Open-label Safety Population. Descriptive statistics for double-blind IP compliance will be presented by treatment group for the DBTP for the Double-blind Safety Population.

#### **9.7.5 Efficacy Analyses**

All efficacy analyses for the OLTP will be performed using the Open-label mITT Population. All efficacy analyses for the DBTP will be performed using the Double-blind mITT Population. The baseline of the lead-in study will be used as the baseline for the OLTP and the DBTP. All statistical tests will be 2-sided hypothesis tests performed at the 5% level of significance and all confidence intervals (CIs) will be 2-sided 95% CIs, unless stated otherwise.

An additional analysis plan specific to European Medicines Agency will be presented in a stand-alone document.

**9.7.5.1 Primary Efficacy Analyses**

The primary efficacy parameter is the time to first relapse during the 52 weeks of the DBTP, defined as the number of days from the randomization date of DBTP to the relapse date during the 52 weeks of the DBTP. Relapse during the DBTP is defined as meeting any of the following criteria:

- MADRS total score  $\geq 18$  at 2 consecutive visits
- $\geq 2$  increase in CGI-S score compared with that obtained at randomization
- Risk of suicide as determined by the investigator
- Need for hospitalization due to worsening of depression as determined by the investigator
- Need for alternative treatment of depressive symptoms as determined by the investigator

For patients who did not meet the above relapse criteria during the 52 weeks of the DBTP, the time to relapse will be censored at the time of completion or discontinuation from the study, or 52 weeks, whichever is earlier.

The primary efficacy analysis will compare the time to first relapse between placebo and rapastinel treatment groups in the respective time-frame (within the 52 weeks of the DBTP) using the log-rank test. The primary null hypothesis is that the distribution of the time to relapse for each of the rapastinel treatment groups is not different from that for the placebo treatment group.

Estimates of the hazard ratio and 95% CI will be based on the Cox proportional hazards model with treatment group as an explanatory variable. The cumulative distribution function of time to relapse will be characterized by the Kaplan-Meier curves.

The Hochberg procedure will be used to control the overall type I error rate at the 0.05 level for comparisons between each of rapastinel treatment groups and the placebo.

[REDACTED]

• [REDACTED]

[REDACTED]

[REDACTED]

[REDACTED]

[REDACTED]

[REDACTED]

[REDACTED]

[REDACTED]

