### 9.4.5 Selection of Dosages in the Study

The doses of rapastinel in this study were selected based on 2 Phase 2 clinical studies in patients with MDD, in which single IV doses of rapastinel 5 mg/kg and 10 mg/kg were shown to produce marked antidepressant effects within 1 day that lasted approximately 1 week or longer in responding patients.

A 450-mg IV unit dose is expected to be appropriate for most patients as this represents a dose of 4.5 mg/kg in a 100-kg patient and a dose of 9 mg/kg in a 50-kg patient.

A 225-mg IV unit dose (equivalent to 2.25 mg/kg in a 100-kg patient and a dose of 4.5 mg/kg in a 50-kg patient) is available only to patients entering from RAP-MD-30 to allow for further evaluation of the dose-response profile after multiple dosing.

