#### 8.0 EFFICACY ANALYSES

#### 8.1 PRIMARY EFFICACY PARAMETERS

The analysis of the primary efficacy parameter will be performed using the Double-blind mITT Population.

The primary efficacy parameter is the time to first relapse during the 52 weeks of the DBTP, defined as the number of days from the randomization date of DBTP to the relapse date (ie., relapse date – randomization date + 1). Relapse during the DBTP is defined as meeting any of the following criteria:

- Rater-administered MADRS total score  $\geq 18$  at 2 consecutive visits
- $\geq 2$  increase in CGI-S score compared with that obtained at randomization
- Risk of suicide as determined by the investigator
- Need for hospitalization due to worsening of depression as determined by the investigator
- Need for alternative treatment of depressive symptoms as determined by the investigator

Patients who did not meet the above relapse criteria during the 52 weeks of the DBTP, the time to relapse will be censored at the time of completion or discontinuation from the study, or 52 weeks, whichever is earlier.

The primary efficacy analysis will be presented by the cumulative distribution function of time to relapse characterized by the Kaplan-Meier curve for each treatment group.

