## 14.11 STRATIFICATION HANDLING CONVENTIONS

Stratification is not being implemented in this study.

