#### 15.0 CHANGES TO ANALYSES SPECIFIED IN PROTOCOL

Analyses and output have been limited to those needed to support the writing of an abbreviated CSR. The major changes to the analyses specified in the original protocol, dated 02MAY2018, are as follows:

• The primary efficacy analysis will be performed via the Kaplan-Meier curve for the cumulative distribution function of time to relapse for each treatment group.

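### The protocol's primary test and hazard ratio leave MADRS at randomization unused; adjusting for it is a cheap efficiency gain, not a repair of validity

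*Protocol*

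**What the plan says.** Protocol 9.7.5.1 tests time to first relapse over 52 weeks by log-rank, each rapastinel group against placebo, and names no strata. The hazard ratio comes from a "Cox proportional hazards model with treatment group as an explanatory variable"; no other term is named. Protocol 9.7.5 states: "All statistical tests will be 2-sided hypothesis tests performed at the 5% level of significance". For the two comparisons, 9.7.5.1 adds: "The Hochberg procedure will be used to control the overall type I error rate at the 0.05 level". SAP 14.11 states: "Stratification is not being implemented in this study".

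The SAP no longer carries this inference in its readable text. SAP 15.0 limits the output to what an abbreviated report needs and lists as a major change: "The primary efficacy analysis will be performed via the Kaplan-Meier curve for the cumulative distribution function of time to relapse for each treatment group". SAP 8.1 says the same and names no log-rank test, Cox model or Hochberg step. SAP 12.0 still repeats the protocol's power statement.

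**The concern.** Several baseline facts are fixed before randomization and already recorded: the open-label dose, the lead-in study and the MADRS total score. Dose and lead-in study overlap, because the 225 mg dose "is available only to patients entering from RAP-MD-30" (Protocol 9.4.5) and, by SAP 2.0, RAP-MD-31 supplied nobody.

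MADRS at randomization is the variable of interest because it lies on the same scale as the endpoint. Patients must score 12 or less at two consecutive visits before randomization (Protocol 9.1.1), and one relapse criterion is 18 or more at two consecutive visits. A patient randomized at 12 is 6 points below that threshold; one randomized at 2 is 16 points below it. If the score predicts relapse, a comparison that ignores it has less power than an adjusted one, and its hazard ratio lies closer to 1 than the hazard ratio at a given score. What is at stake is some power, mainly where Hochberg leaves one comparison to be tested at 0.025.

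**Working it through.** **1. The plan's own figure.** Inputs from Protocol 9.7.10 and SAP 12.0: 200 per group, placebo relapse 19% and dropout 20% per 26 weeks, hazard ratio 0.475, 52 weeks, alpha 0.05 (two-sided by Protocol 9.7.5). Exponential times are assumed.

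- Weekly hazards: placebo −ln(0.81)/26 = 0.00810; rapastinel 0.475 × 0.00810 = 0.00385; dropout −ln(0.80)/26 = 0.00858.
- Event probability λ/(λ+δ) × [1 − exp(−52(λ+δ))]: 28.2% on placebo, 14.7% on rapastinel.
- Events: 200 × (0.2817 + 0.1474) = 85.8.
- Freedman: z = √85.8 × (1 − 0.475)/(1 + 0.475) − 1.96 = 1.34, power 90.9%. Lachin-Foulkes gives 91.2% and Schoenfeld 93.2%.

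The stated 90% reproduces with no covariate.

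**2. Effect of adjusting.** The same inputs were simulated with one standard-normal baseline score, a hazard ratio of 0.475 at a fixed score, and overall placebo relapse held at 19% per 26 weeks. The score's prognostic strength is an assumption. Power is for one comparison at two-sided 0.05. "Unadjusted" is the log-rank test or the treatment-only Cox model; where both were run they agree within 0.5 point. The two main runs have 3,000 trials per setting (simulation error about 0.5 point per power figure). Several figures in a cell come from separate runs.

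| Relapse HR per SD (SD of log hazard) | Unadjusted % | Adjusted Cox % | Gain, points |
|---|---|---|---|
| 1.00 (0) | 92.7 | 92.4 | −0.3 |
| 1.28 (0.25) | 91.7 | 92.2 | 0.5 |
| 1.35 (0.30) | 91.1 | 91.3 | 0.2 |
| 1.65 (0.50) | 90.2; 89.7; 89.9 | 91.6; 91.5; 92.1 | 1.4; 1.8; 2.2 |
| 2.0 (0.69) | 87.3; 88.8 | 91.3; 91.9 | 4.0; 3.1 |
| 2.12 (0.75) | 86.0 | 90.8 | 4.8 |
| 2.72 (1.0) | 81.9 | 90.6 | 8.7 |

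The last two rows show the trend; nothing in the documents supports a score that strong.

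At 0.025, the level for one comparison if the other fails under Hochberg, power goes from 85.2% to 86.1% at 1.35 per SD, from 83.7% to 86.7% at 1.65 and from 80.5% to 86.4% at 2.0.

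The average unadjusted hazard ratio is 0.471 with no prognostic score, then 0.484, 0.499 and 0.520 at log-hazard SD 0.5, 0.75 and 1.0. The adjusted one stays between 0.466 and 0.472.

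**3. Validity.** With no treatment effect and the score omitted, the log-rank test rejected in 4.8% (SD 0.5) and 5.2% (SD 1.0) of 5,000 trials. The simulation error is √(0.05 × 0.95/5000) = 0.3 point, so type I error is held.

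**4. Stratifying by dose and lead-in study instead.** With three strata assumed at 20/30/50% and not prognostic, 6,000 trials per setting gave, for unstratified and stratified log-rank, 92.6% and 92.2% at 1.35 per SD, 90.6% and 90.4% at 1.65, and 87.8% and 87.6% at 2.0. With stratum hazards assumed to differ 1.25-fold per step, the figures were 90.9% and 91.0%, 89.9% and 90.1%, and 87.8% and 87.9%. There is no gain beyond simulation error, because MADRS never enters that p-value. By numerical integration, omitting a binary factor such as dose, at 15 to 50% prevalence and with hazard ratio 2, costs only 0.6 to 0.8 point.

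**5. Which MADRS value.** Protocol 9.7.5 makes the lead-in study's baseline the baseline for both periods. The SAP 14.2 table footnote takes the last value before the first dose of each period. An unqualified baseline MADRS could therefore mean the lead-in score, which is not the one argued for here.

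**The case against.** The strongest reply is that nothing is broken. An unstratified test after unstratified randomization is valid and consistent. The sample-size text gives 0.475 with no covariates, so its natural reading is an unadjusted hazard ratio, and on that reading planned power is intact; the shortfall in the table arises only if 0.475 is taken as conditional. Prognostic strength is not given anywhere, and the score is truncated at 12. The SAP has also replaced the test with Kaplan-Meier curves. All of this stands and limits the point to efficiency. It does not show that adjustment is worthless: the possible loss is negligible and the possible gain is not.

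A reader might infer more than the documents support:

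- **That the hazard ratio is biased.** The unadjusted estimate targets a marginal effect. Its distance from the conditional one is non-collapsibility, and chance imbalance is already reflected in the standard error and type I error.
- **That the trial is underpowered.** The 90% reproduces.
- **That stratifying the log-rank by dose and lead-in study is the remedy.** Step 4 shows that it does not deliver the gain.
- **That no adjusted analysis is planned.** Text after the Hochberg sentence in 9.7.5.1 is blacked out, and 9.7.5 refers to a separate plan for the European Medicines Agency, so absence cannot be claimed.

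**Conclusion.** The point holds as a modest efficiency recommendation for the protocol's inferential analysis and for any formal comparison that is made. If 0.475 is conditional on the score, adjusting for MADRS at randomization raises single-comparison power at two-sided 0.05 by about 0 to 1 point at a hazard ratio of 1.35 per SD, 1 to 2 points at 1.65 and 3 to 4 points at 2.0, with a simulated difference of −0.3 point, within simulation error, if the score is not prognostic. If 0.475 is the unadjusted value, the planned 90% is already met and adjustment for a prognostic score would add to it. The sizes rest on assumed prognostic strength, exponential times and a normally distributed score; the real score is confined to 0 to 12.

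**What to change.** Wherever a formal comparison is made, state before unblinding that the primary test and the hazard ratio both come from a Cox model with treatment group and MADRS total score at double-blind randomization as a continuous covariate. This means Protocol 9.7.5.1, and SAP 8.1 if inference is reinstated. Define the score as the last value before the first double-blind dose, not the lead-in baseline. Name the test statistic and apply Hochberg to the two adjusted p-values. Adding the covariate to the Cox model while leaving the log-rank as the primary test would not change the p-value.

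Keep the unadjusted log-rank and Cox analyses as supportive. Strata for open-label dose and lead-in study are optional and add little power.

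The cost is a short paragraph and a few lines of code, with no new data or patients; the stability rule already requires MADRS before randomization. In the current SAP, the formal comparison would first have to be put back. If the report stays with Kaplan-Meier curves alone, there is no test to adjust.
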